	14.2.1.2.3	Bar Chart of Proportion of Subjects with EASI-75 at Week 16 - Missing as Non-Responder – Initial Period	ITT Population
	14.2.1.2.6	Sensitivity Analysis of Proportion of Subjects with EASI-75 at Week 16 - Tipping Point Analysis – Initial Period	ITT Population
14.2.2		Key Secondary Efficacy Parameters	
14.2.2.1		Key Secondary Efficacy Parameters: PP NRS Improvement ≥ 4	
	14.2.2.1.5	Sensitivity Analysis of Proportion of Subjects with Weekly Average PP NRS Improvement ≥ 4 at Weeks 1, 2, 4 and 16 - Tipping Point Analysis – Initial Period	ITT Population
14.2.2.2		Key Secondary Efficacy Parameters: PP NRS < 2	
	14.2.2.2.5	Sensitivity Analysis of Proportion of Subjects with Weekly Average PP NRS < 2 at Weeks 4 and 16 - Tipping Point Analysis – Initial Period	ITT Population
14.2.2.3		Key Secondary Efficacy Parameters: SD NRS Improvement ≥ 4	
	14.2.2.3.5	Sensitivity Analysis of Proportion of Subjects with Weekly Average SD NRS Improvement ≥ 4 at Week 16 - Tipping Point Analysis – Initial Period	ITT Population
14.2.2.4		Key Secondary Efficacy Parameter: EASI-75 and PP NRS Improvement ≥ 4 at Week 16	

This document is confidential.

1.0

CD14152:SPR118169:SAP_V01

Approved 10-Nov-2022 00:00:00

Header	Figure Number	Name	Analysis Set
	14.2.2.4.5	Sensitivity Analysis of Proportion of Subjects with EASI-75 and Weekly Average PP NRS Improvement ≥ 4 at Week 16 - Tipping Point Analysis – Initial Period	ITT Population
14.2.2.5		Key Secondary Efficacy Parameter: IGA Success and Weekly Average PP NRS Improvement ≥ 4 at Week 16	
	14.2.2.5.5	Sensitivity Analysis of Proportion of Subjects with an IGA Success and Weekly Average PP NRS Improvement ≥ 4 at Week 16 - Tipping Point Analysis – Initial Period	ITT Population
14.2.3		Secondary Efficacy Parameters	
14.2.3.1		Secondary Efficacy Parameter: IGA	
14.2.3.1.1		Secondary Efficacy Parameter: IGA – Initial Period	
	14.2.3.1.1.5	Line Plot of Proportion of Subjects with IGA Success – Missing as Non-Responder – Initial Period	ITT Population
14.2.3.1.2		Secondary Efficacy Parameter: IGA – Maintenance Period	
	14.2.3.1.2.3	Line Plot of Proportion of Subjects with IGA Success from Initial Baseline – Missing as Non-responder – Maintenance Period	Enrolled Subjects in Maintenance Period Population
14.2.3.2		Secondary Efficacy Parameter: EASI	
14.2.3.2.1		Secondary Efficacy Parameter: EASI –Initial Period	
	14.2.3.2.1.6	Line Plot of Proportion of Subjects with EASI-50, EASI-75, or EASI-90 - Missing as Non-Responder – Initial Period	ITT Population
14.2.3.2.2		Secondary Efficacy Parameter: EASI – Maintenance Period	
	14.2.3.2.2.4	Line Plot of Proportion of Subjects with EASI-50, EASI-75, and EASI-90 from Initial Baseline – Missing as Non-Responder - Maintenance Period	Enrolled Subjects in Maintenance Period Population
14.2.3.3		Secondary Efficacy Parameter: PP NRS	
14.2.3.3.1		Secondary Efficacy Parameter: PP NRS – Initial Period	
	14.2.3.3.1.5	Line Plot of Proportion of Subjects with Weekly Average PP NRS Improvement ≥ 4 - Missing as Non-Responder – Initial Period	ITT Population
	14.2.3.3.1.7	Line Plot of Proportion of Subjects with Weekly Average PP NRS < 2 - Missing as Non-Responder – Initial Period	ITT Population
14.2.3.3.2		Secondary Efficacy Parameter: PP NRS – Maintenance Period	
	14.2.3.3.2.3	Line Plot of Proportion of Subjects with Weekly Average PP NRS Improvement ≥ 4 from Initial Baseline – Missing as Non-Responder - Maintenance Period	Enrolled Subjects in Maintenance Period Population

This document is confidential.

1.0

CD14152.SPR118169.SAP.V01

Approved 10-Nov-2022 00:00:00

Header	Figure Number	Name	Analysis Set
	14.2.3.3.2.6	Line Plot of Proportion of Subjects with Weekly Average PP NRS < 2 – Missing as Non-Responder - Maintenance Period	Enrolled Subjects in Maintenance Period Population
14.2.3.7		Secondary Efficacy Parameter: SD NRS	
14.2.3.7.1		Secondary Efficacy Parameter: SD NRS – Initial Period	
	14.2.3.7.1.3	Line Plot of Subjects with Weekly Average SD NRS Improvement ≥ 4 - Missing as Non-Responder – Initial Period	ITT Population
14.2.3.7.2		Secondary Efficacy Parameter: SD NRS – Maintenance Period	
	14.2.3.7.2.3	Line Plot of Proportion of Subjects with Weekly Average SD NRS Improvement ≥ 4 from Initial Baseline – Missing as Non-Responder - Maintenance Period	Enrolled Subjects in Maintenance Period Population
14.2.3.22		Rescue Therapy Used	
14.2.3.22.1		Rescue Therapy Used – Initial Period	
	14.2.3.22.1.3	Kaplan Meier Curve for Time to First Rescue Therapy Used - OC - Initial Period	ITT Population
14.2.3.22.2		Rescue Therapy Used – Maintenance Period	
	14.2.3.22.2.3	Kaplan Meier Curve for Time to First Rescue Therapy Used - OC - Maintenance Period	Enrolled Subjects in Maintenance Period Population
14.2.3.23		Relapse – Maintenance Period	
	14.2.3.23.2	Kaplan Meier Curve for Time to First Relapse- OC - Maintenance Period	Enrolled Subjects in Maintenance Period Population
14.2.4		Pharmacokinetics	
	14.2.4.3	Mean Nemolizumab Time-Concentration Profiles - Initial Period	PK Population
	14.2.4.4	Mean Time-Concentration Profiles - Maintenance Period	Enrolled PK Subjects in Maintenance Period Population
14.3.4		Laboratory Value	
14.3.4.1		Clinical Laboratory Data	
14.3.4.1.2		Blood Chemistry Data	
	14.3.4.1.2.10	Distribution of Aspartate Aminotransferase (AST) by Visit with Maximum Post- Baseline Values – Initial Period	Safety Population
	14.3.4.1.2.11	Distribution of Aspartate Aminotransferase (AST) by Visit with Maximum Post-Maintenance Baseline Values – Maintenance Period	Enrolled Safety Subjects in Maintenance Period Population
	14.3.4.1.2.12	Distribution of Alanine Aminotransferase (ALT) by Visit with Maximum Post-Baseline Values – Initial Period	Safety Population
	14.3.4.1.2.13	Distribution of Alanine Aminotransferase (ALT) by Visit with Maximum Post-Maintenance Baseline Values – Maintenance Period	Enrolled Safety Subjects in Maintenance Period Population

This document is confidential.

Header	Figure Number	Name	Analysis Set
	14.3.4.1.2.14	Distribution of Alkaline Phosphatase (ALP) by Visit with Maximum Post-Baseline Values – Initial Period	Safety Population
	14.3.4.1.2.15	Distribution of Alkaline Phosphatase (ALP) by Visit with Maximum Post-Maintenance Baseline Values – Maintenance Period	Enrolled Safety Subjects in Maintenance Period Population
	14.3.4.1.2.16	Distribution of Total Bilirubin by Visit with Maximum Post-Baseline Values – Initial Period	Safety Population
	14.3.4.1.2.17	Distribution of Total Bilirubin by Visit with Maximum Post-Maintenance Baseline Values – Maintenance Period	Enrolled Safety Subjects in Maintenance Period Population
	14.3.4.1.2.18	Distribution of Creatinine Phosphokinase by Visit with Maximum Post-Baseline Values – Initial Period	Safety Population
	14.3.4.1.2.19	Distribution of Creatinine Phosphokinase by Visit with Maximum Post-Maintenance Baseline Values – Maintenance Period	Enrolled Safety Subjects in Maintenance Period Population
14.3.4.2		Vital Signs	
	14.3.4.2.6	Distribution of Vital Signs by Visit with Maximum Post-Baseline Values – Initial Period	Safety Population
	14.3.4.2.7	Distribution of Vital Signs by Visit with Maximum Post-Maintenance Baseline Values – Maintenance Period after Initial Period	Enrolled Safety Subjects in Maintenance Period Population

This document is confidential.

21. Index of Listings

Header	Listing Number	Name	Analysis Set
16.2		Subject Data Listings	
16.2.1		Discontinued Subjects	
	16.2.1.1	Randomization	ITT Population
	16.2.1.2	Study Completion Status	ITT Population
	16.2.1.3	Screen Failures	Screened Subjects
	16.2.1.4	Study Drug Completion Status	ITT Population
	16.2.1.5	Visit Dates	ITT Population
	16.2.1.6	Missing Visits Due to COVID-19	ITT Population
	16.2.1.7	Missing Assessment due to COVID-19	ITT Population
	16.2.1.8	Covid-19 relevant comments	ITT Population
16.2.2		Protocol Deviations	
	16.2.2.1	Protocol Deviations	ITT Population
	16.2.2.2	Protocol Deviations Related to COVID-19	ITT Population
16.2.3		Subjects Excluded from Analysis Sets	
	16.2.3.1	Subjects in Analysis Populations	ITT Population
	16.2.3.2	Inclusion and Exclusion Criteria Not Met	Screened Subjects
16.2.4		Demographic Data	
	16.2.4.1	Demographics and Baseline Characteristics	ITT Population
	16.2.4.2	Baseline Disease Characteristics	ITT Population
	16.2.4.3	Medical History	ITT Population
	16.2.4.4	Medical and Surgical Procedures	ITT Population
	16.2.4.5	Rescue Medical and Surgical Procedures	ITT Population
	16.2.4.6	Prior and Concomitant Medications	ITT Population
	16.2.4.7	Rescue Medications	ITT Population
	16.2.4.8	Background Therapy Medications	ITT Population
	16.2.4.9	Background TCI/TCS Dispensation and Recipient	ITT Population
	16.2.4.10	Subjects with Difference between Randomization Stratification and Actual Stratification	ITT Population
16.2.5		Compliance and Exposure Information	
	16.2.5.1	Study Drug Dispensation	Safety Population
	16.2.5.2	Study Drug Administration	Safety Population
	16.2.5.3	Study Drug Compliance	Safety Population
	16.2.5.4	Nemolizumab Serum Concentrations	PK Population
16.2.6		Individual Efficacy Response Data	
	16.2.6.1	Investigator's Global Assessment (IGA)	ITT Population
	16.2.6.2	Eczema Area and Severity Index (EASI)	ITT Population
	16.2.6.3	Weekly Average Pruritus and CCI CCI Numeric Rating Scale	ITT Population
		CCI	

This document is confidential.

1.0

CD14152.SPR118169.SAP.V01

Approved 10-Nov-2022 00:00:00

Header	Listing Number	Name	Analysis Set
	CCI		
16.2.7		Adverse Event Listings	
	16.2.7.1	Treatment Emergent Adverse Events (TEAE)	Safety Population
	16.2.7.2	Pre-Treatment Adverse Events	Safety Population
	16.2.7.3	Treatment Emergent Adverse Events (TEAE)	Safety Population – Subjects with COVID-19 Infection
	16.2.7.4	Treatment Emergent Adverse Events (TEAE) comments	Safety Population
	16.2.7.5	Adjudicated Asthma Treatment Emergent Adverse Events (TEAE)	Safety Population
	16.2.7.6	Adjudicated Asthma Treatment Emergent Adverse Events (TEAE) Comments by Independent Adjudication Committee	Safety Population
16.2.8		Listing of Individual Laboratory Measurements by Subject	
16.2.8.1		Clinical Laboratory Data	
	16.2.8.1.1	Laboratory Data - Hematology	Safety Population
	16.2.8.1.2	Laboratory Data – Clinical Chemistry	Safety Population
	16.2.8.1.3	Laboratory Data - Urinalysis	Safety Population
	16.2.8.1.4	Childbearing Potential and Premenses Status	Safety Population
	16.2.8.1.5	Pregnancy Test Results	Safety Population
	16.2.8.1.6	Tuberculosis Test Results	Safety Population
	16.2.8.1.7	Virology	Safety Population
16.2.8.2		Other Safety Data	
	16.2.8.2.1	Vital Signs, Height and Weight	Safety Population
	16.2.8.2.2	Electrocardiogram (ECG)	Safety Population
	16.2.8.2.3	Physical Examination	Safety Population
	16.2.8.2.4	Respiratory Assessment – Medical Interview	Safety Population

This document is confidential.

Statistical Analysis Plan for Interventional Studies

Sponsor: Galderma Research & Development, LLC; Protocol No.: RD.06.SPR.118169

Header	Listing Number	Name	Analysis Set
	16.2.8.2.5	Respiratory Assessment – Peak Expiratory Flow (PEF)	Safety Population
	16.2.8.2.6	Known Asthma, Wheeze, Dyspnea and Cough Triggers	Safety Population
	16.2.8.2.7	Asthma Control Test (ACT)	Safety Population
	16.2.8.2.8	Subjects with a drop by $\geq 15\%$ from Baseline for either PEF or ACT	Safety Population
	CCI		

1.0

CD14152:SPR118169:SAP.V01

Approved 10-Nov-2022 00:00:00

This document is confidential.

22. Appendices

22.1. Tipping point analysis and Multiple imputation (MI) methods

Prior to conducting tipping point analysis and MI imputation, subjects with data after the receipt of rescue therapy will be considered treatment failure i.e., non-responder for analysis. Tipping point analysis and MI imputation will be performed for subjects with real missing data which is not induced by the receipt of rescue therapy.

Tipping point analysis will be performed by converting non-responders due to missing data to responders in successive increments (Δ) for both treatment groups to assess the robustness of analysis. The value of Δ that overturns (i.e. non-significant) the primary results will represent the tipping point. A graphic display of all possible combination of the number of responders among both treatment groups will be presented.

Multiple imputation (MI) methods for missing data. The MI imputation will be carried out as follows.

1. Imputation Phase
 - a. A 50 imputed datasets with a monotone missing pattern will be created using SAS MI procedure based on the observed data (Markov-Chain-Monte-Carlo method, MCMC). The seed to be used is 118169 (the Protocol number). Pattern of missing data will be evaluated and it is expected that the pattern of missing data will be monotonic. For non-monotone missing data patterns, MCMC method of MI procedure will be used to impute enough data so that the remaining missing data is monotone.
 - b. Each of the imputed datasets will be used to generate 50 complete datasets, using following approaches:
 - i. Ordinal data (e.g., IGA score): A logistic regression method to impute the ordinal missing data, including treatment, randomization strata, and assessments from earlier time points as covariates. Potential auxiliary variables (e.g., the number of injections) may be explored and added into the imputation model. Response or total score of the subjects will be derived using these imputed data.
 - ii. Continuous data (e.g., EASI score): A linear regression model including treatment, randomization strata, and assessments from earlier time points as covariates will be used to impute the score. Potential auxiliary variables (e.g., the number of injections) may be explored and added into the imputation model. Response or total score of the subjects will be derived using these imputed data.
2. Analysis Phase: The analysis will be conducted using the complete datasets.
 - a. Binary endpoint: The complete datasets will be modelled for the endpoint using CMH method. Proportion of responders in each treatment arm, difference and standard error will be calculated.
 - b. Continuous endpoint: The complete datasets will be analyzed using ANCOVA including treatment group and randomization stratification factors as factors and appropriate Baseline values as a covariate, if applicable. LSM means in each treatment arm, difference and standard errors will be calculated.
3. Pooling Phase: The results from the analysis phase will be combined as follows.
 - a. Binary endpoint: The results from the CMH analysis of the multiple imputed datasets will be combined using the Rubin (1987) and Li et al (1991) approach to produce pooled CMH statistics

This document is confidential.

and p-value. Proportion of responders in each treatment arm, difference and standard error will be combined using the MIANALYZE procedure in SAS.

- b. Continuous endpoint: The LSMeans in each treatment arm, difference and standard errors from the ANCOVA of the multiple imputed datasets will be combined using the MIANALYZE procedure in SAS.

22.2. Example SAS Code

1. The example SAS code for CMH model is listed as below:

```
Proc freq data=analysis_data;  
  
    Tables stratum*trt*resp/ cmh alpha=0.1;  
Run;
```

2. The example SAS code for MMRM model is listed as below:

```
Proc mixed data = analysis_data;  
  
    class stratum trtp avisit subjid;  
    model chg = base stratum trtp avisit trtp*avisit base*avisit / ddfm=kr;  
    repeated avisit / subject=subjid(trtp) type=un;  
    lsmeans trtp/ cl diff;  
    lsmeans trtp*avisit/ slice=avisit cl diff;  
run;
```

3. The example SAS code for ANCOVA model is listed as below:

```
Proc mixed data = analysis_data;  
    class stratum trtp;  
    model chg = base stratum trtp;  
    lsmeans trtp/ cl diff;  
run;
```

4. The example SAS code for imputation phase by PROC MI:

```
proc mi data=analysis_data seed=118169 minimum=0 maximum=xx nimpute=50 out=out_data;  
    mcmc impute=monotone nbiter=200 niter=100;  
    var base stratum y4 y8 y12 y16;  
run;  
  
Proc mi data = analysis_data seed=118169 minimum=0 maximum=xx nimpute=number_of_imputations  
out=out_data;  
    class trtp stratum;  
    monotone reg (/details);  
    var base stratum y4 y8 y12 y16;  
run;
```

This document is confidential.

For IGA,

```
Proc mi data = analysis_data seed=118169 minimum=0 maximum=xx nimpute=number_of_imputations
out=out_data;
  class trtp stratum;
  monotone logistic (/details);
  var base stratum y4 y8 y12 y16;
run;
```

5. The example SAS code for pooling phase for ANCOVA model by PROC MIANALYZE:

```
proc sort data=diff; by avisitn trtp; run;
proc sort data=ism; by avisitn trtp; run;
proc mianalyze data=diff; by avisitn trtp;
modeffects estimate;
stderr stderr;
ods output ParameterEstimates=estdiff; run;
```

```
proc mianalyze data=ism; by avisitn trtp;
modeffects estimate;
stderr stderr;
ods output ParameterEstimates=estism; run;
```

1.0

CD14152.SPR118169.SAP.V01

Approved 10-Nov-2022 00:00:00

This document is confidential.

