### 8.5.1 Early Termination Visit

Subjects may discontinue from the study or discontinue the study treatment only and continue to participate in the study.

Subjects who prematurely discontinue from the study should undergo final study assessments according to the following guidelines:

- Subjects discontinued from the study during the initial treatment period on/before the Week 16 visit should attend an ET visit. A follow-up/final visit is required 12 weeks after the last study drug administration.
- Subjects discontinued from the study during the maintenance period should attend an ET visit.

A follow-up/final visit is required 12 weeks after the last study drug administration.

Subjects who prematurely discontinue the study drug will be asked to continue participation in the study and return for all remaining visits and assessments (including daily assessment of pruritus, sleep disturbance, etc). Participation will continue until the subject completes the final study visit or otherwise discontinues study participation.

Subjects requiring rescue medication (with or without study medication discontinuation) may be eligible for LTE study participation:

- Subjects requiring rescue medication during the initial treatment period should

CONFIDENTIAL

continue with study visits including the Visit 6/Week 16. A follow-up/final visit is not required for subjects participating in the LTE study.

- During the maintenance period, for subjects requiring rescue medication before the Week 32 visit, a wait period with continuing study visits until the Week 32 visit is due is required. Thereafter, no wait period is required. Subjects must complete the final study/ET assessments prior to rollover to the LTE study.

A follow-up visit is not required for subjects who will participate in the LTE.

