### 10.1.10 Sensitivity Analyses for Primary and Key Secondary Endpoints

The following sensitivity analyses will be conducted for the robustness of the analyses.

- Same analysis on Per-protocol population
- **Tipping point analysis** will be performed by converting non-responders due to missing data to responders in successive increments ( $\Delta$ ) for both treatment groups to assess the robustness of analysis. The value of  $\Delta$  that overturns (ie, non-significant) the primary results will represent the tipping point. A graphic display of all possible combination of the number of responders among both treatment groups will be

CONFIDENTIAL

presented.

- **Multiple imputation (MI) methods** for missing data: The MI imputation will be carried out as follows.
  1. Imputation Phase
    - a. A 50 imputed datasets with a monotone missing pattern will be created using SAS MI procedure based on the observed data (Markov-Chain-Monte-Carlo method, MCMC). The seed to be used is 118169 (the Protocol number). Pattern of missing data will be evaluated and it is expected that the pattern of missing data will be monotonic. For non-monotone missing data patterns, MCMC method of MI procedure will be used to impute enough data so that the remaining missing data is monotone.
    - b. Each of the imputed datasets will be used to generate 50 complete datasets, using the following approaches:
      - i. *Ordinal data (eg, IGA score)*: A logistic regression method to impute the ordinal missing data, including treatment, randomization strata, and assessments from earlier time points as covariates. Response or total score of the subjects will be derived using these imputed data.
      - ii. *Continuous data (eg, EASI score)*: A linear regression model including treatment, randomization strata, and assessments from earlier time points as covariates will be used to impute the score. Response or total score of the subjects will be derived using these imputed data.
  2. Analysis Phase: The analysis will be conducted using the complete datasets.
    - a. *Binary endpoint*: The complete datasets will be modelled for the endpoint using CMH method as per analysis described in Section 10.1.3 . Proportion of responders in each treatment arm, difference and standard error will be calculated.

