Intercurrent Event	Strategy to Deal With Intercurrent Event Within Analysis	Assessment of Subject
Treatment discontinuation	Treatment policy	Use observed response

This document is confidential.

Table 7-2: Estimands for Co-primary Endpoints (2 endpoints)

[figure not shown]
Endpoints	Estimands
Proportion of subjects with an IGA success (defined as an IGA of 0 [clear] or 1 [almost clear] and a \geq 2-point reduction from Baseline) at Week 16	Population: ITT population (Full population; Baseline PP NRS \geq 7)
	Endpoint: a binary response indicates if subjects have IGA of 0 [clear] or 1 [almost clear] and a \geq 2-point reduction from Baseline at Week 16
	Intercurrent events: use of rescue therapies prior to Week 16 is considered as non-responder; the observed response at Week 16 after treatment discontinuation will be used in the analysis.
	Summary measure: treatment difference of nemolizumab and placebo in response rate
Proportion of subjects with EASI-75 (\geq 75% improvement in EASI from Baseline) at Week 16	Population: ITT population (Full population; Baseline PP NRS \geq 7)
	Endpoint: a binary response indicates if subjects with at least 75% improvement in EASI from baseline at Week 16
	Intercurrent events: use of rescue therapies prior to Week 16 is considered as non-responder; the observed response at Week 16 after treatment discontinuation will be used in the analysis.
	Summary measure: treatment difference of nemolizumab and placebo in response rate

Table 7-3 Estimands for Key Secondary Endpoints (9 endpoints)

Endpoints	Estimands
Proportion of subjects with an improvement of PP NRS \geq 4 at Week 16	Population: ITT population (Full population; Baseline PP NRS \geq 7)
	Endpoint: a binary response indicates if subjects have IGA of 0 [clear] or 1 [almost clear] and a \geq 2-point reduction from Baseline at Week 16
	Intercurrent events: use of rescue therapies prior to Week 16 is considered as non-responder; the observed response at Week 16 after treatment discontinuation will be used in the analysis.
	Summary measure: treatment difference of nemolizumab and placebo in response rate
Proportion of subjects with PP NRS < 2 at Week 16	Population: ITT population (Full population; Baseline PP NRS \geq 7)
	Endpoint: a binary response indicates if subjects with PP NRS < 2 at Week 16

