8.4. Analysis Visit Windows

Efficacy by-visit summaries will use the analysis visit. Unscheduled and early termination visits will be windowed based on the following analysis visit window which is based on study day. If multiple measurements are taken within the same window, the one taken closest to the target study day will be used for the analysis. If there are multiple measurements with same difference from target day, the later assessment should be used for the analysis.

Table 8-1: Analysis Visit Window

Analysis Visit	Target Study Day	Visit Window for EASI, IGA, CCI
Baseline	1	<=1
Week 4	29	2 to 42
Week 8	57	43 to 70
Week 12	85	71 to 98
Week 15	106	NA
Week 16	113	99 to 126
Week 20	141	127 to 154
Week 24	169	155 to 182
Week 28	197	183 to 210
Week 32	225	211 to 238
Week 36	253	239 to 266
Week 40	281	267 to 294
Week 44	309	295 to 322

This document is confidential.

Week 48	337	>=323	CCI
---------	-----	-------	-----

CCI Visit window after Week 16 will not be applicable for PIQs.

CCI

For the diary data at post-baseline visit, only the diary data assessed within the timeframe below (+1 hour to end time in spec) will be considered for analysis. If >1 diary recorded on a day (within window), only one of them to take for analysis (i.e. latest one for evening diary, earliest one for morning diary).

- Evening assessment (PP/CCI NRS, CCI recorded from 17:00:00 to 00:59:59 CCI

Consecutive daily assessment:

For the evening assessments (PP NRS, CCI) during Initial Period, the daily data collected up to Week 16 will be classified into analysis visits considering the data during the 7 days immediately preceding the target study day of analysis visit. Similarly, for the morning assessment (CCI) during Initial Period, the 7 days data up to the target study day will be classified into analysis visit. Details of the analysis visit window are in the table below. Only the data belongs to Initial Period will be considered for classifying the analysis visit in Initial Period.

Table 8-2: Analysis Visit Window for Evening and Morning Assessments during Initial Period

Analysis Visit	Target Study Day of Analysis Visit	Visit Window for evening assessment (PP NRS, CCI)	CCI
Baseline*	1	-7 to -1	
Week 1	8	1 to 7	
Week 2	15	8 to 14	
Week 3	22	15 to 21	
Week 4	29	22 to 28	
Week 5	36	29 to 35	
Week 6	43	36 to 42	
Week 7	50	43 to 49	
Week 8	57	50 to 56	
Week 9	64	57 to 63	
Week 10	71	64 to 70	
Week 11	78	71 to 77	
Week 12	85	78 to 84	
Week 13	92	85 to 91	

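### The monotone PROC MI examples in SAP 22.2 leave treatment out of the imputation model that SAP 22.1 and protocol 10.1.10 require; if followed, they pull the MI treatment difference toward zero

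*SAP*

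**What the plan says.** SAP 22.1, step 1b, specifies the imputation model for ordinal scores such as IGA: "A logistic regression method to impute the ordinal missing data, including treatment, randomization strata, and assessments from earlier time points as covariates". The model for continuous scores such as EASI has the same covariates. Protocol 10.1.10, step 1b, agrees: "A linear regression model including treatment, randomization strata, and assessments from earlier time points as covariates will be used to impute the score". Step 1a, which uses MCMC to reach a monotone missing pattern, names no covariates in either document.

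SAP 22.2 gives three PROC MI examples: MCMC, monotone regression, and monotone logistic for IGA. Each prints the variable list "var base stratum y4 y8 y12 y16". In the two monotone blocks trtp is in the CLASS statement, but it is not in VAR. There is no BY trtp, and the MONOTONE statements carry no formula. Both monotone blocks name the same input dataset as the MCMC block, not its output. The IGA block's CLASS statement holds only trtp and stratum.

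On the number of datasets, 22.1 says: "Each of the imputed datasets will be used to generate 50 complete datasets".

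SAP section 15 lists one departure from the protocol, the definition of concomitant therapy, and nothing on imputation. The SAP does not say whether 22.1 or 22.2 governs if they differ.

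**The concern.** CLASS declares a variable's type; it does not make the variable a covariate. With no formula, a MONOTONE step predicts each variable from those that precede it in VAR. As printed, Week 16 scores would be imputed from baseline, stratum and earlier visits, with the arms pooled. The analysis model then estimates a treatment effect that the imputation model left out, so imputed values in the two arms are drawn together and the difference shrinks.

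Two groups of analyses use this appendix: the MI sensitivity analyses of the co-primary and key secondary endpoints (SAP 10.1.2 and 10.2), and the ANCOVA with MI for continuous secondary endpoints (SAP 10.3). A sensitivity result weakened by a coding omission could be misread as a lack of robustness to missing data.

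**Working it through.** **Inputs from the documents.** EASI-75 49% v 19% and IGA success 30% v 12% at Week 16; 750 subjects at 2:1, so 500 and 250; 15% dropout in the initial period (protocol 10.2; SAP 4.3 except the dropout rate). Two-sided 2.5% level (SAP 10.1.1).

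**Check of the plan's own figure.** SAP 4.3 claims more than 99% power. For two proportions with pooled variance under the null,

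power = Φ{[d − z × √(p̄(1−p̄)(1/n1 + 1/n2))] / √(p1q1/n1 + p2q2/n2)}, with z = 2.2414.

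- IGA: p̄ = (500×0.30 + 250×0.12)/750 = 0.24. Null SE = √(0.24×0.76×0.006) = 0.0331. Alternative SE = √(0.21/500 + 0.1056/250) = 0.0290. Argument = (0.18 − 0.0741)/0.0290 = 3.65, so power is 99.99%.
- EASI-75: the same steps give above 99.99%.
- With 15% fewer subjects (425 and 212.5), IGA power is 99.92%.

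The stated figure reproduces, so the inputs are sound.

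**Bound on the shrinkage.** Suppose a fraction f in each arm is imputed and these subjects have no post-baseline data. A pooled model gives them the same expected response in both arms, so the expected difference is (1−f) × d.

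| f | EASI-75 | IGA success |
|---|---|---|
| 5% | 0.95 × 30 = 28.5 | 0.95 × 18 = 17.1 |
| 15% | 0.85 × 30 = 25.5 | 0.85 × 18 = 15.3 |

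**Simulation between the bound and zero loss.** Earlier visits carry some information on treatment, so the loss is usually smaller than the bound. The same simulated data were imputed with and without treatment by sequential regression on baseline, stratum and the four visits (500:250, 400 replicates, 5 imputations each).

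Assumptions not in the documents: AR(1) visit correlation of 0.5 or 0.8; 40/70/90/100% of the Week 16 effect present at Weeks 4/8/12/16; dropout independent of outcome and equal in the arms; IGA handled as a latent continuous score. Only the monotone step was simulated, and rescue was not modelled. At 15% imputed, differences in points, with treatment → without:

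| Endpoint, correlation | All drop out before Week 4 | Even over visits | All after Week 12 |
|---|---|---|---|
| EASI-75, 0.5 | 29.9 → 25.5 | 29.8 → 26.2 | 29.9 → 27.8 |
| EASI-75, 0.8 | 30.1 → 25.6 | 30.1 → 27.3 | 30.3 → 29.2 |
| IGA, 0.5 | 18.1 → 15.3 | 17.8 → 15.6 | 18.0 → 16.7 |
| IGA, 0.8 | 17.7 → 15.0 | 17.9 → 16.2 | 18.1 → 17.5 |

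With treatment in the model, MI recovers the assumed 30 and 18 points. Without it, the loss runs from 3.5% (IGA: 0.63/18.14; EASI-75: 1.05/30.25) to about 15% (IGA: 2.70/17.67; EASI-75: 4.49/30.08). The IGA value of 15.0 lies just under the 15.3 bound because that set of replicates averaged 17.7, not 18. The Monte Carlo SE of each contrast is at most 0.06 points.

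**Dependence on the amount missing** (EASI-75, even dropout, correlation 0.5): loss of 1.2 points at 5% imputed, 3.6 at 15% and 7.1 at 30%; 4.9 points if dropout is 10% on active and 25% on placebo.

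**How much will be imputed.** The documents give no figure. It may fall below 15%, because MI applies only to "real missing data which is not induced by the receipt of rescue therapy" (SAP 22.1). Subjects who stop study drug "will be asked to continue participation in the study and return for all remaining visits" (protocol 8.5.1), and "the observed response at Week 16 after treatment discontinuation will be used in the analysis" (SAP section 7). "Unscheduled and early termination visits will be windowed based on the following analysis visit window" (SAP 8.4), which can also fill a Week 16 value.

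**The case against.** The strongest reply is that 22.1 is the specification, it is right, and it is what SAP 10.1.2 and 10.3 cite. Section 22.2 is headed as example code. It contains placeholders for the maximum and the number of imputations, and its CMH example prints an alpha of 0.1 that fits neither of the interval levels in SAP 10.1.1. A programmer must rewrite it, and checking against 22.1 could catch the omission. This stands, and it makes the harm conditional. It does not remove the mismatch: the blocks carry the trial's own seed, 50 imputations in the MCMC step and the IGA/EASI visit schedule, and the MMRM and ANCOVA examples beside them do include trtp in the model.

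It also stands that MI has no part in the gatekeeping, that the MI-ANCOVA secondary analyses are not multiplicity-controlled, and that the bias runs against the drug.

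A reader might infer more than the documents support:

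- **That significance of the IGA sensitivity test would be lost, especially in the PP NRS ≥ 7 population.** The printed IGA block could not run as intended, since MONOTONE LOGISTIC imputes classification variables and the visit scores are not in CLASS. A significance rate would describe some other program. It would also depend on that population's size, for which the plan gives only a minimum of 250.
- **That the loss can be sized for POEM or PP NRS.** POEM is collected at Weeks 8 and 16 and PP NRS is averaged weekly. Neither fits the printed list, so any figure would describe code that is not in the SAP.
- **That the MCMC block contradicts the text.** Step 1a names no covariates. Leaving treatment out there is undesirable, but it is not a contradiction.
- **That the plan calls for 50 × 50 = 2,500 datasets, or restarts from unimputed data.** The wording allows the first reading without requiring it, and the repeated dataset name may be a placeholder. Both need clarifying; neither adds to the size of the problem.

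**Conclusion.** The mismatch is real and confined to step 1b: the text in both documents requires treatment, the two monotone examples omit it, and no change is declared. If the examples are followed, the MI difference moves toward zero. At 15% imputed the loss is about 3.5 to 15%, leaving EASI-75 at about 25.5 to 29.2 points instead of 30 and IGA at about 15.0 to 17.5 instead of 18. These sizes rest on the assumed correlations, build-up of effect and dropout timing, and on dropout that is equal between arms and unrelated to outcome. In the even-dropout case run at 5% the EASI-75 loss was 1.2 points.

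The primary non-responder analysis and the MMRM analyses are untouched. This should be fixed because the SAP holds two incompatible imputation models without ranking them. It does not threaten the trial's main conclusions.

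**What to change.** In SAP 22.2:

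- Put trtp in VAR ahead of y4 to y16 in both monotone steps.
- In the IGA block, also put y4 to y16 in CLASS so that MONOTONE LOGISTIC can impute them.
- In the MCMC step, use a numeric treatment indicator or run BY trtp.
- Run the monotone step on the MCMC output BY _imputation_ with nimpute=1, giving 50 datasets in total.

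In SAP 22.1, reword the sentence on complete datasets to match that total, and state that 22.1 prevails over the example code.

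The cost is a few lines of code and text. Conduct, data collection and sample size do not change.
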